2. HYPOTHESIS AND OBJECTIVES

We propose a pilot randomized comparative effectiveness trial comparing respiratory complications and inflammatory markers based on MV settings of 8-10 ml/kg pbw and higher Vt of 14-16 ml/kg pbw in people with acute cervical SCI in an acute inpatient rehabilitation hospital. Our **long-term goal** is to study optimal ventilator settings and treatment approaches in acute SCI to reduce infections and improve lifelong outcomes.

Objectives:

Objective 1: To compare MV outcomes of high vs. low Vt on the relative risk of pneumonia in the acute rehabilitation hospital.

Objective 2: To generate the feasibility data to inform the future RCT design. To achieve this objective, we will obtain the following data: a) Recruitment rate: the proportion of eligible people who provide consent (b) Adherence rate: the proportion of participants in each group who receive assigned intervention per protocol; (c) Retention rate: the proportion of participants in each group who complete all study procedures prior to discharge from our hospital; d) Missing data: Percentage of missing data in each group.

Objective 3: To analyze MV related lung injury inflammatory biomarkers in relation to tidal volume and outcomes.

Hypothesis:

Hypothesis 1: We hypothesize that Bayesian analysis will indicate a>70% probability of lower risk of pneumonia in people with acute cervical SCI receiving lower Vt MV than higher Vt.

Hypothesis 2: We hypothesize that we will be able to recruit **at least** 80% of eligible people each year and among recruited subjects, adherence and retention rate will be 80%, with less than 10% missing data on outcome measures.

Hypothesis 3.1: We hypothesize that MV-related lung injury inflammatory biomarkers (IL-1, IL6, IL-8, and tissue necrosis factor α levels) in serum and tracheal aspirate would be lower in the low Vt MV group compared to high Vt.

Hypothesis 3.2: People with acute cervical SCI receiving MV will have higher inflammatory markers levels than people with acute cervical SCI who do not require mechanical ventilation.

Hypothesis 3.3: People with acute cervical SCI independent of mechanical ventilation status who have higher inflammatory marker levels are more likely to develop pneumonia and other respiratory complications.

Potential Risks and Benefits:

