3. STUDY POPULATION

Sample Size: We plan to recruit 45 subjects (15 in low Vt, 15 in high Vt, and 15 in the control group). We will recruit 30 adults with acute cervical SCI admitted on mechanical ventilation from TIRR MHH and Craig Hospital and an additional 15 people with acute cervical SCI not dependent on mechanical ventilation at admission to serve as controls from TIRR MHH.

Criteria for Recruitment: All consecutive patients with SCI admitted to TIRR MHH and Craig Hospital will be screened for eligibility based on inclusion and exclusion criteria during the study period. The screening will involve the review of history from the patient or primary admitting clinician. If a patient meets eligibility criteria, the research coordinator will provide further information on the study, answer any questions, and recruit if they are willing to participate and provide consent.

Inclusion Criteria: Subjects must meet all of the inclusion criteria listed below to participate in this study.

- Adult patients \geq 18 years (Lung volumes and ventilator settings are different for ages <18 years).
- Acute SCI of duration \leq four months
- Mechanical ventilation subjects: traumatic or non-traumatic cervical SCI with neurological level C1-C5 admitted to our acute inpatient rehabilitation facility (AIR) on mechanical ventilation.
- Control subjects: traumatic cervical SCI admitted to our acute inpatient rehabilitation facility (AIR) who are not dependent on mechanical ventilation.

Exclusion Criteria: All subjects meeting any of the exclusion criteria listed below at baseline will be excluded from participation.

- Severe dysphagia due to concomitant brain stem injury, which increases the risk of pneumonia
- Severe brain injury resulting in dysphagia and inability to follow instructions to perform vital capacity measurements
- ARDS or severe lung disease (required supplemental oxygen or ventilator prior to SCI) at the time of admission (these conditions will not allow patients to randomize because target Vt may below)
- Prolonged antibiotics for > 3 weeks at the time of admission due to infection (e.g., osteomyelitis, epidural abscess, etc.),
- Presence of diaphragmatic pacemaker.

Withdrawal Criteria: Possible reasons for discontinuation of study intervention: Intolerance to proposed ventilator settings.

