Outcomes: The **primary outcome is pneumonia episodes** with evidence of new or progressive and persistent infiltrate on chest radiograph plus 2 of the following abnormal white blood cell count, presence of fever or hyperthermia, purulent sputum, and deterioration in gas exchange.²¹ Any new pneumonia episodes which meet the above criteria and developed 48 hrs after achieving target Vt will be recorded. New pneumonia events can only be recorded after 14 days from the onset of the first event.

The **secondary outcomes** include feasibility outcomes. We will obtain the following data: a) **Recruitment rate:** the proportion of eligible people who provide consent (b) **Adherence rate:** the proportion of participants in each group who receive assigned intervention per protocol; (c) **Retention rate:** the proportion of participants in each group who complete all study procedures and d) **Missing data:** Percentage of missing data in each group. Based on only one RCT²⁵ performed in SCI comparing high vs. low Vt, we anticipate a total recruitment rate of 80% (i.e., that 80% of the eligible would consent for the study), and of those who are enrolled in the study, 80% adherence and retention rate will be observed. We anticipate <10% missing data.

Additional outcomes: This data will be collected from the time of admission to our rehabilitation hospital until discharge. a) b) **Other respiratory complications:** The following ventilator-associated events will be reported: transfer to acute care hospital due to respiratory complications, weaning failure, new pneumothorax, ARDS, pleural effusion, pulmonary embolism, atelectasis, and pulmonary edema, and c) total ventilator days, weaning days and hospital length of stay.

We will perform an analysis of MV-related lung injury biomarkers. Blood and tracheal aspirate samples will be collected at 3-time points; at baseline within 48 hrs of admission to AIR facility, 48- 72 hrs after achieving target Vt, and 3rd sample post- weaning or 2 weeks from target Vt. Samples will be processed and stored at -80 ° C until use in [name] laboratory located at the Medical School, University of Texas in Houston, TX. We will focus on IL-1, IL-6, IL-8, and TNF- α levels. For controls we will obtain blood samples within 48 hrs of admission and 2 weeks from baseline.

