Additional data: Additional data collection will include age, sex, weight, height, date of injury, date of admission to AIR, time since injury, mechanism of injury, American Spinal Injury Association (ASIA) impairment scale (AIS), vital capacity at admission, maximum vital capacity achieved during AIR stay, ventilator settings including Vt, peak and plateau pressure, hospital length of stay and discharge location. We will also collect information on any other ongoing or new infectious events other than pneumonia.

Randomization: Each subject will be randomized to either a tidal volume of 8-10 ml/kg pbw or 14-16 ml/kg pbw within 48 hrs of admission after obtaining consent. A 1:1 allocation ratio will be applied with permuted block size to maintain blindness and balance. Subjects will be stratified based on C1-C3 AIS A to ensure equal allocation of those with the most severe respiratory impairment and unlikely to wean from the vent. In our experience, C1-C3, AIS A was associated with lower vital capacity at admission. The study research assistant will randomize subjects in the redcap database, and he/she will not be involved in data analysis.

Blinding: The principal investigator (PI), statistician, outcome assessors, and participants will be blinded to tidal volume assignment.

Study Visits and Procedures:

Screening: Patients will be screened at the time of admission to TIRR Memorial Hermann. Respiratory therapist and SCI attendings will notify PI or research assistant (RA) regarding admits of an SCI patient dependent on mechanical ventilation or cervical SCI patients who are not dependent on MV (controls). PI or RA will discuss eligibility with respiratory therapists or attending physicians. PI may review discharge summary from acute care hospital or history and physical performed at TIRR admission to determine eligibility. If a person doesn't meet eligibility criteria, we will not save any identified data other than deidentified information on the reason for screening failure.

The screening will require information on age, past medical and surgical history, the duration of SCI, etiology of SCI, the dependence on a ventilator, neurological level and current medications.

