Aim 2: The number of patients contacted and recruited per month will be presented, and we will use the CONSORT diagram to summarize the numbers and reasons related to recruitment, follow-up, and dropout. The main feasibility outcomes include recruitment rate, adherence rate, and retention rate.

We will summarize these outcomes by arm using frequency and percentage. We will inspect these percentages relative to our feasibility targets.

Aim 3: Individual inflammatory marker levels will be presented as mean with standard deviation. A linear mixed model will be constructed on cytokine levels, adding time and randomization group as factors in the model. In this model, the interaction between time and group will be used to study differences over time between groups. A random intercept for the patient will be included to account for within-patient correlation. If the residuals are not normally distributed in linear mixed model analyses, the data will be transformed (e.g., natural logarithm), or an alternative distribution will be used. The relation between cytokine levels and the development of pneumonia or pulmonary adverse events will be studied with a multivariate logistic regression analysis. A risk ratio with 95% confidence interval (95% CI) will be presented

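### The ventilated-versus-control comparison of marker levels (Hypothesis 3.2) has no clearly stated model and gives no role to time since injury, which the trial already collects

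*Combined protocol and SAP*

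**What the plan says.** Section 2 states Hypothesis 3.2 as a comparison of levels: "People with acute cervical SCI receiving MV will have higher inflammatory markers levels than people with acute cervical SCI who do not require mechanical ventilation". Section 3 sets the numbers: "We plan to recruit 45 subjects (15 in low Vt, 15 in high Vt, and 15 in the control group". Under Section 5, only the two ventilated arms are randomised. Controls are recruited separately, from one of the two hospitals.

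The eligibility rule "Acute SCI of duration" up to four months applies to everyone, with no lower limit and no matching between groups. The stratification factors in Sections 5 and 6 (vital capacity in one, injury level and completeness in the other) concern the ventilated arms and do not involve time since injury.

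Section 6 times every sample from rehabilitation admission, from reaching target tidal volume or from baseline, never from injury. For controls: "For controls we will obtain blood samples within 48 hrs of admission and 2 weeks from baseline". The additional data in the same section include "date of injury, date of admission to AIR, time since injury".

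The Aim 3 text in Section 11 gives one cytokine model: "A linear mixed model will be constructed on cytokine levels, adding time and randomization group as factors in the model". Group differences over time are read from the time-by-group interaction, and a random intercept handles repeated samples. No covariate is named. The logistic regression that follows serves the relation between cytokines and pneumonia.

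**The concern.** Randomisation protects the low-versus-high tidal volume comparison (Hypothesis 3.1). It does nothing for Hypothesis 3.2, where the groups are formed by clinical status. Two baseline samples, each taken within 48 hours of admission, can be weeks or months apart in injury phase. The model's time factor is most naturally the sample occasion, so it does not capture this.

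If ventilated patients arrive later and markers fall after injury, a real ventilation effect is diluted or hidden. If they arrive earlier, an effect can appear where there is none. Section 1 says the pilot should help identify markers of lung injury in this population, so a marker could be picked up or dropped because of when patients were sampled.

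**Working it through.** **The plan's own figure.** There is no power or precision figure for this contrast to reproduce. The total of 15 + 15 + 15 = 45 was set on feasibility.

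**Inputs from the documents.** 30 ventilated patients and 15 controls; injury up to four months old; shared blood sampling at baseline and about two weeks later (days 14–18 in both schedules).

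**Inputs assumed, because the documents give none.** Residual SD of the log marker 1.0; SD of time since injury 20 days; marker half-life h of 30 or 60 days; ventilated patients sampled Δ = 7, 14 or 28 days later after injury. One value per patient is used.

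**Step 1: bias of the level contrast.** Let log marker = a + δ·(ventilated) − k·(days since injury) + error, with k = ln 2 / h. The unadjusted group difference is δ − k·Δ, so the marker ratio is multiplied by 2^(−Δ/h).

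**Step 2: false significance with no true effect.** The unadjusted residual SD is √(1 + k²·20²), which is 1.102 for h = 30 and 1.026 for h = 60. Multiplying by √(1/30 + 1/15) = 0.316 gives standard errors of 0.348 and 0.325. The false-positive rate comes from a noncentral t with 43 degrees of freedom and noncentrality kΔ/SE.

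| h (days) | Δ (days) | kΔ | Spurious ratio | kΔ/SE | False significance |
|---|---|---|---|---|---|
| 30 | 7 | 0.162 | 0.85 | 0.46 | 7% |
| 30 | 14 | 0.323 | 0.72 | 0.93 | 15% |
| 30 | 28 | 0.647 | 0.52 | 1.86 | 44% |
| 60 | 7 | 0.081 | 0.92 | 0.25 | 6% |
| 60 | 14 | 0.162 | 0.85 | 0.50 | 8% |
| 60 | 28 | 0.323 | 0.72 | 1.00 | 16% |

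If ventilated patients were instead sampled 14 days earlier (h = 30), the spurious ratio would be 2^(14/30) = 1.38. With Δ = 0, or with no trend, the ratio is 1.

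**Step 3: a true two-fold excess, h = 30.** The unadjusted ratio is 2 × 0.85, 2 × 0.72 and 2 × 0.52, that is 1.70, 1.45 and 1.05. Power is 32%, 18% and 5%. With time since injury in the model the expected ratio is 2.0 and power is about 56%, 53% and 43%. In simulation the adjusted false-positive rate stayed at about 5%.

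**Step 4: the planned interaction.** Take two samples 14 days apart. Under the trend in Step 1 each group changes by −14k, whatever the gap, so the gap cancels. Simulated false positives for the interaction stayed near 5%. The cancellation is exact only for that shape. Suppose the log marker falls by b per unit of log days, with baseline at day 30 in controls and day 44 in ventilated patients (assumed). The level bias is then b·ln(44/30) = 0.38b, and the interaction bias is b·[ln(44/30) − ln(58/44)] = 0.11b.

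**Step 5: cost of adjusting when there is no trend.** The standard error grows by 1/√(1 − r²), where r² = (2/9)Δ² / [(2/9)Δ² + 400] and 2/9 = (30/45)(15/45). For Δ = 7, 14 and 28 days the factor is 1.01, 1.05 and 1.20. Power for a two-fold effect falls from 57% to about 56%, 53% and 43%.

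**The case against.** The strongest objection is that the stated model draws its conclusion from the interaction, which a log-linear trend leaves unbiased. A reader might infer from the table that the planned interaction test has a false-positive rate of up to 44%. The documents do not support that: those figures belong to a level contrast, which Section 11 never writes down. Hypothesis 3.2 is nevertheless about levels, and a test of differential change does not answer it.

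Second, the model names the randomization group, so it may not be meant for controls at all. That is fair. The gap is then wider, because Hypothesis 3.2 has no model.

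Third, the documents show no group difference in time since injury. A reader might assume that ventilated patients arrive later, and so that the direction of bias is known. Nothing in the plan says so, and the striking figures need both a long gap and a short half-life.

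Fourth, other imbalances are written into eligibility. Ventilated patients may have non-traumatic injury and come from two hospitals; controls have traumatic injury and come from one. Adjusting for time since injury leaves these in place.

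Fifth, arrival time may itself depend on being ventilated. The adjusted estimate then answers a narrower question, a comparison at the same injury phase, and needs overlap between the groups. This is a reason to show both estimates.

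Finally, this is a small pilot and the markers are additional outcomes. That lowers the stakes, but a small sample does not reduce bias.

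**Conclusion.** The point holds for the level contrast in Hypothesis 3.2. That contrast is not randomised, the only cytokine model does not clearly cover it, and a collected variable that may confound it is given no role. The bias is slope times gap, in a direction the documents do not show. Under the assumed values the spurious ratio runs from 0.92 to 0.52 if ventilated patients are sampled later, with false significance of 6% to 44%. It vanishes if either the gap or the trend is zero.

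The point does not extend to the randomised comparison in Hypothesis 3.1, where allocation balances time since injury in expectation. It extends to the interaction only so far as the trend departs from log-linear. It is worth correcting before the marker data are analysed; it does not threaten the trial's primary or feasibility aims.

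**What to change.** In Aim 3, state Hypothesis 3.2 as a ventilated-versus-control contrast in blood marker level at the two shared times (baseline and about two weeks), with time since injury at baseline sampling as a prespecified continuous covariate, for example log days. Report the distribution of time since injury in each group, the overlap between groups, and the unadjusted estimate beside the adjusted one. If overlap is poor, say that the adjusted estimate relies on extrapolation. Adding the same term to the Hypothesis 3.1 comparison is optional.

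This takes a sentence or two and no new data. The price is one degree of freedom and a wider interval: about 20% more standard error under an assumed 28-day gap, SD 20 days and no marker trend, and about 5% more at 14 days. It does not deal with differences in hospital or cause of injury, which need their own statement.

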5. STUDY DESIGN

We propose a randomized comparative effectiveness trial to study systematically current Vt ranges to determine optimal settings to improve outcomes. Study participants will be randomly assigned to high tidal volume (14-16 ml/kg pbw) or low tidal volume of 8 to 10 ml/kg pbw within 48 hrs of admission. Subjects will be stratified based vital capacity at admission (≥ 5.8 cc/kg pbw) to ensure equal allocation of those with the most severe respiratory impairment and unlikely to wean from the vent. In our experience, vital capacity ≥ 5.8 cc/kg pbw was associated with higher odds of weaning. We will screen and recruit an additional 15 people with acute SCI not dependent on mechanical ventilation at admission to serve as controls. We anticipate 3 years to complete study recruitment. A 1:1 allocation ratio will be applied to the mechanical ventilation groups. Participants, principal investigator, outcome assessors, and statistician will be blinded to tidal volume assignment.

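### The Aim 3 interaction compares the randomised Vt arms on change from baseline; adjusting for baseline and naming one post-target contrast would give a more precise answer from the same samples

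*Combined protocol and SAP*

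**What the plan says.** Hypothesis 3.1 (Section 2) is directional and concerns level: the markers "in serum and tracheal aspirate would be lower in the low Vt MV group compared to high Vt". It names no time point and no size of difference.

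Section 6 (Outcomes) sets the sampling for ventilated patients: "Blood and tracheal aspirate samples will be collected at 3-time points; at baseline within 48 hrs of admission to AIR facility". The second sample follows attainment of target Vt. The third is taken after weaning or two weeks from target.

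Section 11 (Aim 3) gives the model: "A linear mixed model will be constructed on cytokine levels, adding time and randomization group as factors in the model". It continues: "In this model, the interaction between time and group will be used to study differences over time between groups". The covariance is simple: "A random intercept for the patient will be included to account for within-patient correlation".

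Section 3 plans 15 patients in each Vt arm, and Section 5 states: "A 1:1 allocation ratio will be applied to the mechanical ventilation groups".

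Nothing in the protocol enters baseline as a covariate, holds the two randomised arms to one baseline mean, or names the contrast that answers Hypothesis 3.1. For this model it gives no significance level, SD, correlation or effect size.

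**The concern.** Randomisation makes the expected pre-treatment marker level the same in both Vt arms. A model with group, time and their interaction nevertheless estimates a separate baseline mean for each arm. Each post-target interaction term is then the arm difference at that sample minus the arm difference at baseline. This fixes the coefficient on baseline at 1, whatever the data say about how strongly baseline predicts later levels, and carries avoidable baseline sampling noise into the treatment estimate.

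There is a second, conditional point. Time is a factor with three sampling occasions, so the interaction between two arms and time has 2 degrees of freedom. If it is tested as a whole, one degree of freedom goes to whether the arms differ in how sample 2 compares with sample 3. Hypothesis 3.1 asks only whether levels are lower in the low Vt arm.

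With 15 per arm, precision is scarce. Section 1 also gives identifying lung-injury markers as one purpose of the pilot, so a wider interval than necessary weakens what it can pass on to the larger trial.

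**Working it through.** **No figure to reproduce.** The protocol gives no power or precision for Aim 3. The 30 randomised patients are an accrual target: 10–12 per year × 3 years = 30–36, which agrees with 30.

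**Inputs.** From the documents: n = 15 per arm, 1:1 allocation, three samples, random intercept (equal correlation rho between any two samples of a patient). Assumed, because not given: rho of 0.3, 0.5 and 0.7; SD = 1 at every sample, so effects are in SD units; two-sided 5%; complete data.

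**Step 1, variance at one post-target sample (per patient).**
- Change from baseline: 1 + 1 − 2·rho = 2(1 − rho).
- Baseline-adjusted: 1 − rho².
- Ratio, adjusted to change: (1 − rho²) / [2(1 − rho)] = (1 + rho)/2.

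**Step 2, variance for the mean of samples 2 and 3.**
- Change: (1 + rho)/2 + 1 − 2·rho = 1.5(1 − rho).
- Adjusted: (1 + rho)/2 − rho² = (1 − rho)(1 + 2·rho)/2.
- Ratio: (1 + 2·rho)/3.

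| rho | ratio, one sample | n per arm for change to match 15 adjusted | ratio, mean of two | n per arm to match |
|---|---|---|---|---|
| 0.3 | 0.65 | 15/0.65 = 23.1 | 0.53 | 28.1 |
| 0.5 | 0.75 | 20.0 | 0.67 | 22.5 |
| 0.7 | 0.85 | 17.6 | 0.80 | 18.8 |

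Simulation at 15 per arm, which includes the cost of estimating the baseline slope, gives one-sample ratios of about 0.67, 0.78 and 0.88. A further consequence of step 1 is that below rho = 0.5 the change variance 2(1 − rho) exceeds 1, so the change contrast is then less precise than ignoring baseline altogether.

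**Step 3, the extra degree of freedom (only if the test is joint).** Take a constant effect of 0.8 SD and keep the change contrast. The noncentrality is 15 × 0.64 / [2 × 1.5(1 − rho)] = 3.2/(1 − rho), that is 4.57, 6.40 and 10.67. Power with 1 df is 56%, 70% and 89%. With 2 df (2 and 56) it is 45%, 59% and 82%.

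**Step 4, both effects together.** Simulated power, 20,000 trials per setting, for rho 0.3 / 0.5 / 0.7:

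| Effect at sample 2 / sample 3 (SD) | joint 2-df interaction | adjusted, mean of samples 2 and 3 | adjusted, sample 2 only |
|---|---|---|---|
| 0.8 / 0.8 | 44 / 59 / 82% | 79 / 83 / 93% | 58 / 66 / 83% |
| 0.8 / 0.4 | 35 / 46 / 69% | 55 / 59 / 73% | 59 / 66 / 83% |
| 0.4 / 0.8 | 35 / 46 / 69% | 55 / 59 / 74% | 19 / 22 / 30% |

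With no effect, all three tests reject about 5% of the time.

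**Step 5, timing of baseline.** Section 6 (Study procedures for MV group) puts the baseline specimen on Day 1-2 and titration of tidal volume on Day 1-4. The windows overlap. A specimen taken after titration begins is not pre-treatment, and equal expected means can no longer be assumed for it.

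**The case against.** A time-by-group mixed model is conventional and valid. It does use the baseline sample, by subtracting it, and above rho = 0.5 that beats ignoring baseline. The text describes studying differences over time and specifies neither a joint F test nor a decision rule, so per-sample interaction estimates fit it equally well. The markers belong to Objective 3 and to the additional outcomes of a trial sized on feasibility, so no primary or feasibility conclusion depends on them. All of this stands.

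Three stronger readings are tempting and are not supported:
- A reader might infer that the plan discards baseline. It does not; what is missing is conditioning on baseline or an equal-baseline constraint.
- A reader might infer that the 2-df test is the plan's stated test. It follows only if the interaction is tested as a whole.
- A reader might infer that sample 2 alone is the right test, because some patients may already be weaned at sample 3. Hypothesis 3.1 names no time point and Section 6 ranks neither post-target sample. If the difference emerges late (last row of the table), the sample-2 test has 19–30% power against 35–69% for the joint interaction.

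The objection does not remove the variance loss from free baseline means. That loss holds for any rho below 1 and does not depend on the time course of the effect.

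**Conclusion.** The point holds as one of efficiency. The planned contrast is unbiased with nominal type I error, so nothing here suggests a wrong or misleading test. It is less precise than a baseline-adjusted contrast by a factor of (1+rho)/2 in variance at one sample, and (1+2·rho)/3 for the mean of two. The loss shrinks as rho rises and can be modest: at rho 0.7 with effects 0.8/0.4 SD, power goes only from 69% to 73%.

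The variance ratios rest on the random-intercept structure the plan states, equal SDs across samples, and an assumed rho. The power figures also rest on assumed effect sizes and time courses, and the comparison with the interaction assumes a joint test. Under the three time courses tried, the adjusted average of both post-target samples had more power than the joint interaction every time (55–93% against 35–82%); the sample-2-only test did not.

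The finding concerns the two randomised arms only. The non-ventilated controls are not randomised, and an equal-baseline assumption has no basis for them. It is a minor improvement to a non-primary aim.

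**What to change.** In Section 11, Aim 3, for the low versus high Vt comparison:
- Fit the mixed model with one common baseline mean: time effects plus group-by-time terms at samples 2 and 3, with no group main effect. Alternatively, model samples 2 and 3 with baseline as a covariate. Keep the planned transformation if residuals require it.
- Prespecify one low-minus-high post-target contrast with its interval as the answer to Hypothesis 3.1, preferably the average of samples 2 and 3, and report each sample alongside.
- Keep the non-randomised controls out of this constraint.
- Reconcile the Section 6 lines on baseline sampling and titration, so that a sample counts as baseline only if it precedes any study change in Vt.

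The cost is a few lines of analysis text and one changed model statement, with no new data. There are two downsides to accept. Any single contrast loses power for some time courses; the average gives up some power to a sample-2 test if the effect fades (55–73% against 59–83% in the 0.8/0.4 case). And any sample drawn after titration has started cannot serve as baseline, which matters in a comparison of 30 patients.
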